2. STUDY DESIGN

This is an exploratory, prospective, multicenter, open-label, single-arm, interventional, Phase IIb study designed to explore the associations over time between clinical assessments, multimodal imaging assessments, AH biomarker patterns, and genetic polymorphisms in patients with DME who are treated with faricimab (RO6867461). All DME patients enrolled will be treatment-naïve in the study eye. Hypothesis-generating

signals will be assessed via associations in visual function, retinal anatomy, and AH protein/metabolite composition. State-of-the-art imaging technologies and new immunoassay platforms will be utilized in this study. Advanced analytics and multivariate analysis will also be used to show the relationships between AH and imaging biomarkers as well as genetic polymorphisms.

- AH taps from the study eye will be collected on Day 1 (baseline) and the Day 112 visit (i.e., prior to injections 1 and 5).
- Multimodal retinal imaging will be applied at the screening visit, Day 1 (baseline), and throughout the study (see Appendix 2)

Approximately 35 global study sites will enroll approximately 80 patients who are treatment-naïve in the study eye. However, the Sponsor may increase the sample size up to 100 patients, to compensate for those patients who completed the study without having a full set of Day 1 (baseline) and Day 112 visit analyzable AH samples collected. The aim of this increase is to achieve 60 patients with analyzable Day 1 (baseline) and Day 112 visit AH samples (see Section 2.3). The Sponsor may decide to stop the enrollment as soon as the target of 60 analyzable sets of AH samples is reached. Patients will receive 6 doses (one 6 mg faricimab IVT injection Q4W) starting at Day 1 and ending on the Day 140 visit. Patients will return for a safety follow-up visit (SFV) after ≥28 days and within <35 days following their last study treatment. Patients who discontinue from the study or treatment early (prior to the SFV) but have not withdrawn consent (and have not been lost to follow-up) should return for an early termination visit (ETV) after ≥28 days have elapsed following their last study treatment (visit should occur within <35 days of the patient's last study treatment).

Data from adaptive optics (AO) instruments will be collected from selected study sites that have the technology available. The purpose of this data collection is to conduct a feasibility test of AO for future studies.

In this study, the ocular inclusion and exclusion criteria for the study eye require an assessment of DR severity as assessed on the ETDRS DRSS (Ip et al. 2012). If both eyes are considered eligible, the eye with the worse BCVA, as assessed at screening, will be selected for the study eye unless the Investigator deems the other eye to be more appropriate for treatment in the study.

Patients who use concomitant medications should continue their use, unless listed as a prohibited therapy for this study. Patients who receive prohibited therapies may be discontinued from the study treatment and/or the study.

Patients who discontinue the study prematurely will not be replaced and will not be allowed to restart study treatment.

The total duration of the study for an individual patient will be approximately up to 203 days (i.e., be approximately 29 weeks) divided as follows:

[figure not shown]
- Screening period: up to 28 days (i.e., up to 4 weeks)
- Treatment period: 140 days (±7 days) (i.e., approximately 20 weeks)
- Safety follow-up period: 28 days to 35 days (i.e., approximately 4 to 5 weeks)

A patient is considered to have completed the study if he/she has completed the last scheduled procedure (i.e. he/she has completed the Safety Follow-up visit) shown in the schedule of assessments.

The end of study (EoS) is defined as the date when the last patient completes their last visit (LPLV). The end of the study is expected to occur approximately 168 to 175 days (i.e., 24 to 25 weeks) after the last patient is enrolled. The total length of the study, from the screening visit of the first patient to the EoS, is expected to be approximately 26 months. Alternatively, the Sponsor may decide to terminate the study at any time; in this case, the termination date will be considered the EoS.

Figure 1 presents an overview of the study design.

Figure 1 Study Design

SV: screening visit BV: baseline visit

X: 6 mg faricimab (RO6867461) IVT injection

SFV: safety follow-up visit AH: aqueous humor tap GB: genomic blood draw VA: visual acuity tests

^{*} Multi-modal imaging detailed in the Schedule of Assessments

2.1 PROTOCOL SYNOPSIS

The Protocol Synopsis is in Appendix 1. For additional details, see the Schedule of Assessments in Appendix 2.

2.2 OUTCOME MEASURES

2.2.1 Exploratory Endpoints

To explore the associations over time between clinical assessments, multimodal imaging assessments, AH biomarker patterns and genetic polymorphisms:

- Proportion of patients with a ≥2-step ETDRS DRSS improvement from baseline over time
- Proportion of patients with a ≥3-step ETDRS DRSS improvement from baseline over time
- Changes from baseline in BCVA (as measured on the ETDRS chart) over time
- Changes from baseline in IRF (intraretinal fluid) over time
- Changes from baseline in SRF (subretinal fluid) over time
- Changes from baseline in CST over time
- · Changes from baseline in multimodal imaging over time including:
 - Central retinal thickness
 - Foveal avascular zone (FAZ) / retinal nonperfusion
 - Vessel density
 - Periphery status (ischemia and proliferation)
 - Microaneurysm location, number, and turnover
 - Ischemic area
- Changes from baseline in AH biomarker patterns over time including:
 - Proteins, including but not limited to: cytokines, chemokines, and growth-, angiogenesis-, and complement-related factors, etc.
 - Metabolites, including but not limited to: lipids, sugars, amino acids, etc.
- Genetic polymorphisms via standard clinical genotyping
- Advanced analytics tools (e.g., artificial intelligence-based tools) for the assessment of clinically relevant features

2.2.2 Pharmacokinetic Endpoints

Not Applicable.

2.2.3 Safety Endpoints

The Safety endpoints are:

- Incidence and severity of adverse events
- Description of ocular assessments
- Study treatment exposure and Anti-VEGF exposure for fellow eye
- Laboratory assessments (only HbA1c assessments)
- Concomitant medication
- Concurrent ocular procedures

2.3 DETERMINATION OF SAMPLE SIZE

In this exploratory study, the sample size is based on practical considerations. Approximately 80 patients were planned to be enrolled in the study. With a minimum of 40 patients, there is approximately 80% power to demonstrate that a correlation of 0.4 is statistically significantly different from 0 (alpha = 0.05). Sample size was calculated to 80 to account (adjust) for exploratory multivariate analyses that may be performed to model clinical outcomes based on multiple AH biomarkers.

The Sponsor has increased the sample size up to 99 patients, to compensate for those patients who completed the study without having a full set of Day 1 (baseline) and Day 112 visit analyzable* AH samples collected. The aim of this increase was to achieve 60 patients with analyzable* Day 1 (baseline) and Day 112 visit AH samples.

* Analyzable refers to the AH samples with no major deviations that will be analyzed by at least one specialty laboratory.

2.4 ANALYSIS TIMING

Only final analysis will be performed at the end of Study once all patients have completed the Week 24 (Day 168 visit) visit or have discontinued from the study prior to Week 24, all data collected through Week 24 are in the database, the data have been cleaned and verified, and the database is locked.

The results of the statistical analyses described in this SAP will be included in a Clinical Study Report (CSR). As this is an open-label study, no formal interim analyses are planned. Nevertheless, exploratory analyses of selected endpoints may be performed during the course of the study (e.g., after all patients have completed the Day 28 visit and the necessary data are available).

3. STUDY CONDUCT

3.1 RANDOMIZATION

Not Applicable

3.2 INDEPENDENT REVIEW FACILITY

All ocular images results are obtained by trained site personnel at the study sites and forwarded to the CRC for independent analysis and/or storage. As part of screening process, the CRCs evaluate Spectral Domain-Optical Coherence Tomography (SD-OCT) images and Color Fundus Photography (FP-7M) to provide an objective assessment of patient eligibility. During the study treatment, the CRCs provide an evaluation of all ocular images including: Ultra-Widefield Color Fundus Photography (UWF-C), Ultra-Widefield Fluorescein Angiography (UWF-FA), Spectral Domain and Swept Source Optical Coherence Tomography (SD-OCT and (if capable) SS-OCT), Spectral Domain or Swept Source Optical Coherence Tomography Angiography (SD-OCTA and SS-OCTA), Color Fundus Photography – Modified 7 Field (FP-7M) and Adaptive Optics (AO; to be collected at selected study sites).

3.3 DATA MONITORING

Not Applicable.

4. STATISTICAL METHODS

For continuous variables, descriptive statistics (e.g., number of patients [n], mean, standard deviation [SD], median, 25th and 75th percentiles, minimum, maximum) will be calculated and summarized.

For categorical variables, the number and percentage in each category will be displayed.

Statistical methods for exploratory endpoints are detailed in the Exploratory Analyses section below.

Unless otherwise specified, statistical tests will be two-sided and the statistical significance level will be 5%. Corresponding 95% CIs will be presented as appropriate. Although multiple statistical tests may be conducted, due to the exploratory nature of the study no adjustments to the Type 1 error rate for multiplicity will be made.

The analyses outlined in this SAP supersede those specified in the protocol.

4.1 ANALYSIS POPULATIONS

4.1.1 Modified Intent-To-Treat Population

The modified intent-to-treat (mITT) population is defined as all patients enrolled in the study that received any amount of study treatment.

4.1.2 Per Protocol Population

Not Applicable.

4.1.3 Pharmacokinetic-Evaluable Population

Not Applicable.

4.1.4 Safety-Evaluable Population

Safety-evaluable population (SE) is defined as all patients enrolled who received at least one injection of study treatment.

4.2 ANALYSIS OF STUDY CONDUCT

The number of patients enrolled will be tabulated by country and site.

Patient disposition information will be summarized as follows:

- Number and percentage of patients enrolled
- Number and percentage of patients in the mITT population and SE population
- Number and percentage of patients who complete study treatment
- Number and percentage of patients who discontinue study treatment and the reasons for study treatment discontinuation
- Number and percentage of patients who complete study
- Number and percentage of patients who discontinue study and the reasons for study discontinuation

Major protocol violations, including violations of inclusion/exclusion criteria collected during the study via PDMS will be summarized.

The impact of COVID-19 will be assessed by summarizing major protocol deviations related to COVID-19 and by summarizing COVID-19 related intercurrent events.

4.3 DEMOGRAPHIC AND BASELINE CHARACTERISTICS

Baseline is defined as the last available measurement obtained on or prior to the day of first dose. Patients with missing baseline assessments will not be imputed.

The following demographic and baseline characteristics will be summarized for the mITT population:

- Age (years) as continuous variable and age in category < 65 years, ≥ 65 years
- Gender (Male and Female)
- Self-reported race and ethnicity
- Region
- Female reproductive status
- Smoking history (never, current, former)
- Diabetes mellitus (Type 1, Type 2)
- Baseline HbA1c as continuous and in category < 6.5 %, ≥ 6.5 < 8 % and ≥ 8%
- Systolic blood pressure (mmHg) as continuous variable and its category <140 mmHg, >=140 and <160 mmHg and >=160 mmHg
- Diastolic blood pressure (mmHg) as continuous variable
- Blood pressure (mmHg) in category (> 160 systolic or > 90 diastolic, <= 140 systolic and <= 85 diastolic and <= 120 systolic and <= 80 diastolic)

Baseline ocular characteristics:

- Baseline ocular characteristics description will be done in study eye and fellow eye (analyzed separately).
 - Study eye selection (Eligible eye (right, left, bilateral) and selected eye (right, left)).
 - Diabetic macular edema (Yes/No) (for fellow eye only)

- Diabetic macular edema status at baseline (Resolved/Ongoing) (for fellow eye only)
- Duration since Diabetic macular edema initial diagnosis Onset (in months) and its category (≤ 3 months and >3 months) (date of baseline visit – onset date of Diabetic macular edema diagnosis +1) / 30.4375.
- Baseline BCVA
- Baseline ocular assessments
 - Center subfield thickness (CST)
 - Macular Ischemic Non-Perfusion (Yes/No): Absence is defined as Total area of capillary non perfusion within the macula of 0 to 0.1 mm2.
 - Macular leakage (Yes/No): Absence is defined as Total area of fluorescein leakage within the macula of 0 mm2
 - Intraocular Pressure (mmHg)
 - Lens status (phakic, pseudophakic, aphakic, other)
 - Global Diabetic retinopathy status (ETDRS scale into 12 step) from Ultra-widefield Fundus Photography (UWF-C)
 - Diabetic retinopathy status (ETDRS scale into 12 step) from Color Fundus Photography (FP-7M

A listing of Demographics and relevant baseline characteristics will be presented.

General medical history and baseline conditions:

For each medical history and baseline conditions recorded medical history (MH), the term entered by the investigator describing the event (the "reported term") will be assigned a standardized term (the "Preferred Term" [PT]) and assigned to a superclass term (the "System Organ Class" [SOC]) on the basis of the MedDRA World Health Organization (WHO) dictionary of terms.

The general medical history and baseline conditions will be summarized by SOC and PT.

Prior ocular surgeries and procedures

The description will be done in the study eye and fellow eye (analyzed separately).

- Did the subject have any prior ocular surgeries or procedures? (Yes/No)
- Prior ocular surgery or procedure was for ocular inflammatory disease (Yes/No)
- Number and percentages of patients per ocular surgeries or procedure. (Radiation therapy / Submacular surgery)

Prior medications

Previous medications (defined as treatment started and ended before start date of trial treatment) will be summarized by frequency tables according to the Anatomic Therapeutic Chemical (ATC) classification system using the WHO Drug dictionary.

Prior Ocular Therapies/Treatments

The description will be done in the study eye and fellow eye (analyzed separately).

- Did the subject have any prior ocular therapies/treatments? (Yes/No)
- Number and percentages of patients by ocular therapies/treatments (Laser Photocoagulation, Photodynamic Therapy Visudyne, Lucentis, Macugen, Avastin, Intravitreal Steroids, Subtenon Steroids, Topical Steroids, Dietary Supplement, Other).

4.4 EXPLORATORY ANALYSIS

The objective of this study is to explore the associations over time between clinical assessments, multimodal imaging assessments, AH biomarker patterns, and genetic polymorphisms of treatment-naïve DME patients treated with faricimab on the basis of the endpoints listed in Section 2.2.1.

All exploratory outcomes will be analyzed in the modified intent-to-treat (mITT) population.

Variables will be summarized descriptively at each timepoint in addition to change from baseline.

Continuous outcomes as Change from baseline at each timepoint will be analyzed using a mixed model for repeated measures (MMRM).

Patients with COVID-19 related intercurrent events will be censored after occurrence of these intercurrent events. COVID-19 related intercurrent events are defined as follows:

- Discontinuation of study treatment due to COVID-19
- Use of any prohibited systemic treatment or prohibited therapy in the study eye due to COVID-19
- Missed dose(s) with potentially major impact on BCVA and anatomical endpoints due to COVID-19
- COVID-19 death

Intercurrent events that are not related to COVID-19 will be handled using a treatment policy where all observed values will be used regardless of the occurrence of the intercurrent event. Those are defined as follows:

- Discontinuation of study treatment due to adverse events (AEs) or lack of efficacy not due to COVID-19
- Use of any prohibited systemic treatment or prohibited therapy in the study eye not due to COVID-19

In addition to the analyses listed in this SAP, the associations between AH biomarkers, imaging and clinical assessments will be analyzed and reported separately. Specifications of these analyses will be detailed in a separate document. These analyses may include but are not limited to univariate summaries, scatterplots and correlation coefficients, pairwise correlation matrices, heat maps.

4.4.1 Exploratory Endpoints

All exploratory endpoints will be analyzed in the study eye, over time from baseline up to week 20 or Safety Follow-up period week 24 if the assessment is available (See Appendix 2: Schedule of Assessments).

4.4.1.1 Ocular and multimodal imaging assessments

Best-corrected visual acuity (BCVA)

BCVA score is based on the ETDRS VA chart assessed at a starting distance of 4 meters. The BCVA score (actual value and change from Baseline) will be summarized over time.

A listing of BCVA score over time will be presented.

Change from Baseline in BCVA score over time will be analyzed using a longitudinal mixed effects model repeated measures (MMRM). The model's fixed effects will include visit along with the following covariates:

- Baseline BCVA score
- Age (continuous)
- Region (U.S/Canada and the rest of the world (ROW))

Visit will be treated as a repeated variable within a patient. Patient and visit will be treated as factor variables. An unstructured variance-covariance structure will be applied to model the within-patient errors. If there are convergence issues with the model, then an AR (1) covariance structure may be fitted. The model will be fitted using the Restricted Maximum Likelihood method (REML). Denominator degrees of freedom will be estimated using Satterthwaite's approximation.

Graphical presentation for least square means and 95% confidence intervals will be used to illustrate trends over time.

Diabetic Retinopathy Severity Score (DRSS)

The ETDRS DRSS score (actual value and change from baseline) assessed from Ultrawidefield Fundus Photography (UWF-C) and from Color Fundus Photography (FP-7M) will be summarized over time presenting the following proportion of patients along with a twosided 95% Clopper-Pearson exact confidence interval:

- Number and percentage of patients with >=2 step ETDRS DRSS improvement from baseline
- Number and percentage of patients with >=3 step ETDRS DRSS improvement from baseline

These proportions will be described graphically (bar chart) to illustrate trends over time

Intraretinal fluid (IRF) and Subretinal fluid (SRF)

The IRF/SRF assessed from Spectral Domain-Optical Coherence Tomography (SD-OCT) will be described as below:

Proportion of patients along with a two-sided 95% Clopper-Pearson exact confidence interval:

 Number and percentage of patients with Absence and Presence of intraretinal fluid over time:

- Absence of IRF is defined as IRF-Cystoid Spaces equals to Absent, or Definite outside center subfield only.
- Presence of IRF is defined as IRF-Cystoid Spaces equals to Questionable, or Definite only noncystoid center subfield involved, or Definite cystoid center subfield involved.
- Number of patients with recurrence of IRF over time (i.e. Number of patients with recurrence of IRF over time are defined as patients with presence of IRF at any of the post baseline timepoints (week 4, week 8, week 12, week 16, week 20 and week 24) regardless of their baseline status..)
- Number and percentage of patients with Absence and Presence of subretinal fluid over time:
 - Absence of SRF is defined as SRF equals to Absent or Definite outside center subfield only.
 - Presence of SRF is defined as SRF equals to Questionable or Definite center subfield involved.
- Number of patients with recurrence of SRF over time (i.e., Number of patients with recurrence of SRF over time are defined as patients with presence of SRF at any of the post baseline timepoints (week 4, week 8, week 12, week 16, week 20 and week 24) regardless of their baseline status.)

Additionally, the time to IRF resolution will be defined as the number of days from Baseline to first absence of IRF. The Kaplan-Meier method will be used to estimate the survival function for the time to first IRF resolution. Kaplan-Meier rates and Greenwood 95% CI using log-log transformation will be presented at week 4, week 8, week 12, week 16, week 20 and week 24. Kaplan-Meier plots (presented as cumulative incidence) will be produced. Patients without IRF resolution, discontinued from treatment, will be censored at the last IRF assessment. The patients with absence of IRF at baseline are not considered at risk, therefore, they will be excluded from the analysis.

The same analysis will be produced for the time to SRF resolution.

Retinal thickness using Spectral Domain-Optical Coherence Tomography (SD-OCT)

The measurement of Central subfield thickness (CST ILM-RPE) (actual value and change from Baseline) will be summarized over time up to week 20 and Safety Follow-up period

week 24). In addition, the change from baseline in CST will be analyzed using a longitudinal MMRM. The model's fixed effects will include visit along with the baseline CST ILM-RPE value, age and region covariates.

The same analyses will be performed on Center Point Thickness (CPT ILM-RPE) and on macular volume (Center SubField Volume ILM-RPE, the center subfield (CSF) is the circular region centered on the anatomic fovea with a radius of 500 microns).

Additionally, the time to first absence of DME will be analyzed. The first absence of DME is defined as the number of days from baseline to first time reaching CST (ILM-RPE) < 305 um. The Kaplan-Meier method will be used to estimate the survival function for the time to first absence of DME. Kaplan-Meier rates and Greenwood 95% CI using log-log transformation will be presented at week 4, week 8, week 12, week 16, week 20 and week 24. Kaplan-Meier plots (presented as cumulative incidence) will be produced.

Patients without absence of DME discontinued from treatment, will be censored at the last CST assessment.

Outcome measures using Ultra-widefield Fluorescein Angiography (UWF-FA)

The UWF-FA imaging type was scheduled at screening post-eligibility visit and week 20. The screening visit will be considered as Baseline visit.

The baseline actual value and change from baseline to week 20 will be summarized for the following endpoints:

- Total area of capillary Non-perfusion within the macula ETDRS grid
- Distance of the capillary Non-perfusion to the Center of Fovea
- Perimeter length of total capillary Non-perfusion
- Total area of capillary Non-perfusion within the eye
- Total area of assessable retina for capillary Non-perfusion
- Total area of visible retina
- Total area of fluorescein leakage within the ETDRS grid
- Distance of the fluorescein leakage to the Center of the Fovea
- Perimeter length of total fluorescein leakage

Total area of leakage within the eye

The following proportion of patients along with a two-sided 95% Clopper-Pearson exact confidence interval will be summarized at Baseline and week 20:

- Number and percentage of patients with absence of macular ischemic non perfusion (capillary loss):
 - Absence defined as total area of capillary non perfusion within the macula of 0 to 0.10 mm²
- Number and percentage of patients with absence of ischemic non perfusion within the Total Retinal Area:
 - Absence defined as total area of Capillary non perfusion within the eye of 0 to 1 mm2
- Number and percentage of patients with absence of Macular leakage:
 - Absence is defined as total area of fluorescein leakage within the macula of 0 mm2

The number of patients and percentage at baseline and week 20 visit will be described for the following endpoints:

- Change in fluorescein leakage within ETDRS grid from Screening Visit
- Absence of New Vessels on Disc (NVD)
- Absence of New Vessels Elsewhere (NVE) within 7 field grid
- Absence of New Vessels Elsewhere (NVE) beyond 7 field grid

Adaptive optics

For Adaptive optics assessments, the number of patients who underwent these assessments at baseline and week 20 visit will be summarized.

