4.4.3 Subgroup Analyses

The exploratory endpoints will be summarized by the following subgroups, provided that they include at least 30 patients:

- Baseline BCVA (≥ 64 letters and ≤ 63 letters)
- Baseline DR severity (<47, ≥ 47- ≤ 53, > 53 ETDRS DRSS)
- Baseline HbA1c (≤ 8 %, > 8 %)
- Age (< 65 years, ≥ 65 years)
- Gender (Female and Male)

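### The only MMRM fallback, an unqualified AR(1), would misstate the visit-level confidence intervals if the spread of change differs between visits

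*SAP*

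**What the plan says.** For change from baseline in BCVA, SAP 4.4.1.1 states: "An unstructured variance-covariance structure will be applied to model the within-patient errors". The one alternative is: "If there are convergence issues with the model, then an AR (1) covariance structure may be fitted". Estimation is by REML, and "Denominator degrees of freedom will be estimated using Satterthwaite's approximation". No heterogeneous structure, intermediate step or empirical standard error is mentioned.

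The output is visit by visit: "Graphical presentation for least square means and 95% confidence intervals will be used to illustrate trends over time". SAP Appendix 2 schedules BCVA at six post-baseline visits. They are the same ones that SAP 4.4.1.1 lists for the fluid analyses: "week 4, week 8, week 12, week 16, week 20 and week 24".

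The models for central subfield thickness (CST), center point thickness and macular volume in the same section state no covariance structure of their own. SAP 4.4.2 plans no sensitivity analysis. SAP 4.7 relies on data missing at random for the MMRM. SAP 4.4.3 summarizes the exploratory endpoints by subgroup, "provided that they include at least 30 patients".

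**The concern.** With six visits, an unstructured covariance has 6 × 7 / 2 = 21 parameters. An AR(1) without qualification has two: one variance and one correlation. The step between them is large, and it discards the visit-specific variances. These are what an interval for a visit mean most depends on.

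Under a common variance, every visit mean gets a standard error built from one pooled SD. If patients' changes spread out over time, the pooled SD is too large for Week 4 and too small for Week 24. The plotted intervals would then understate the uncertainty at the last visit. Because the SAP says the structure may be fitted, and lists nothing else, the choice of any other structure would be made after the data are seen.

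**Working it through.** **Plan's own figure.** There is none on this point. The documents give no SD by visit, no within-patient correlation and no dropout rate. The power statement in SAP 2.3 concerns a correlation coefficient and does not bear on it.

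**Rough anchor for the SD.** Protocol 1.3.2 reports a Phase II difference of 3.6 letters at Week 24 with an 80% CI of 1.5 to 5.6.
- Half-width: (5.6 − 1.5) / 2 = 2.05 letters.
- Standard error: 2.05 / 1.2816 = 1.60.
- Protocol 3.3.2 gives 168 treatment-naïve patients, and Protocol 1.3.2 says they were split equally over three arms. Assuming 168 / 3 = 56 per arm with equal SDs, SD = 1.60 × √(56/2) ≈ 8.5 letters.

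This is one adjusted value at one visit. It says nothing about the trend in SD.

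**Closed form.** Assume complete data and a true SD of s_k at visit k. The AR(1) standard error for each visit mean is then approximately s_p / √n, where s_p is the root mean square of the six SDs. The true standard error is s_k / √n. Coverage of the nominal 95% interval is 2Φ(1.96 × s_p / s_k) − 1.

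Worked example, SD rising linearly from 7 to 12: s_p = √[(49 + 64 + 81 + 100 + 121 + 144) / 6] = √(559/6) = 9.65. At Week 24 the ratio is 9.65 / 12 = 0.804 and coverage is 88.5%. At Week 4 the ratio is 9.65 / 7 = 1.38 and coverage is 99.3%.

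| Assumed SD, Week 4 to Week 24 (linear) | s_p | Coverage, Week 4 | Coverage, Week 24 |
|---|---|---|---|
| 8.5 to 8.5 | 8.50 | 95.0% | 95.0% |
| 8 to 8.5 | 8.25 | 95.7% | 94.3% |
| 7 to 8.5 | 7.77 | 97.0% | 92.7% |
| 8 to 11 | 9.56 | 98.1% | 91.1% |
| 7 to 12 | 9.65 | 99.3% | 88.5% |
| 8.5 to 7 (falling) | 7.77 | 92.7% | 97.0% |

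The root mean square is a close approximation to what an AR(1) fit estimates. The best-fitting AR(1) to SDs of 7 to 12 with constant correlation 0.7 has σ = 9.69, which gives 88.7% at Week 24. A true AR correlation of 0.8 also gives 88.7%. The unequal variance drives the error, not the shape of the correlation.

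**Check by simulated REML fits.** There were 1,000 runs per scenario. The Week 24 SD was 8.5, with an SD ratio (Week 24 to Week 4) of 1.5 and 10% random dropout. The correlation was 0.8 (AR) or 0.7 (exchangeable). All of these except the 8.5 anchor are assumptions. The fits used visit means only, with N − 1 degrees of freedom in place of Satterthwaite.
- AR(1) with model-based errors, Week 24 coverage: 87.9% (N = 99, AR), 90.3% (N = 99, exchangeable), 90.1% (N = 80, AR). The closed form gives 90.1%, and Monte Carlo error is about 1 point.
- Over all scenarios run, with SD ratios from 1 to 2, heterogeneous AR(1) gave 94.0% to 96.4% at every visit. AR(1) with sandwich errors gave 93.9% to 96.5%.
- Half-widths at N = 99, ratio 1.5, AR correlation: AR(1) gives 1.42 letters at Week 4 and 1.47 at Week 24. Heterogeneous AR(1) gives 1.12 and 1.75. The misstatement is therefore about 0.3 letters at each end.

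**The case against.** **The trigger is remote.** The planned structure is unstructured and does not have this defect, and 21 parameters with up to 99 patients should usually be estimable. In simulated REML fits by an EM algorithm, under assumed inputs (SD 7 to 12, correlation 0.7, three covariates, some intermittent missingness), 60 of 60 converged at n = 99 at each of 10% and 20% dropout. At n = 30, 150 of 150 converged at each rate. EM is more forgiving than some optimisers, so this does not prove that the fallback is never reached. The objection largely stands.

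**Subgroups.** A reader might infer that the MMRM will be run in groups near 30 and will often fail there. SAP 4.4.3 says only that endpoints are summarized by subgroup. Subgroup models are possible, but they are not stated.

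**Direction.** A reader might also infer that the last-visit intervals for BCVA and CST will be too narrow. The documents do not support that. They give no SD by visit for either measure. CST falls under treatment and its model adjusts for baseline, so its spread could shrink and the error would reverse.

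**Wording.** The SAP does not call the AR(1) homogeneous or the errors model-based. That is the ordinary reading of an AR(1) with REML and Satterthwaite degrees of freedom and no further qualification.

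**Consequence.** The least-squares-means graph is specified under BCVA only. The descriptive tables also show SDs at every visit, so a careful reader could spot a distortion. The study is single-arm and exploratory, and no decision rule depends on an interval's width.

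What remains is that if the fallback is used with unequal SDs, the intervals are wrong, and a better fallback costs almost nothing.

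**Conclusion.** The point holds conditionally and is minor. It needs three things together: the unstructured fit fails, the AR(1) is homogeneous with model-based errors, and the SD of change differs between visits. Week 24 coverage then lies between 95% (equal SDs) and about 89% (7 to 12 letters) for rising SDs. It is about 93% if the SD rises from 7 to the 8.5 letters that the Phase II figures roughly suggest. The 89% figure needs an SD at Week 24 well above that anchor and a rise of about 70% (12 / 7 = 1.71), so it is one end of a range and not a forecast. With falling SDs the early intervals are the narrow ones. For CST the direction is unknown. The harm is misstated precision by visit, not a false confirmatory claim.

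**What to change.** Replace the AR(1) sentence with a pre-specified order: unstructured, then heterogeneous Toeplitz, then heterogeneous AR(1), moving on only when the fit does not converge. Allow a homogeneous structure only as a last resort, and then with small-sample-corrected sandwich standard errors. Compound symmetry belongs in that last group, because it also assumes equal variances. State that the rule applies to the BCVA, CST, center point thickness and macular volume models.

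The cost is a sentence or two in the SAP and standard software options. The downside lies in the last step. Sandwich errors are less stable in groups near 30. They also do not protect the point estimates under missing-at-random dropout if the covariance is misspecified, which is why the heterogeneous structures come first.
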